#### **5.1.4 Visit 4, Post-op check (IP + 7-10 days)**

*Clinical Work-Flow:*

- Post-op check

#### **5.1.5 Visit 5, Abutment surgery + Impression (IP + 13 weeks, ± 10 days)**

*Clinical Work-Flow:*

- Mucosal incisions
- Removal of cover screws
- Implant stability check. If implant is not stable, an individual decision should be made at the discretion of the Investigator. The recommendation is to let the implant sleep for 2-3 months, and if still not stable, remove and place a new 6.6 mm implant of wider diameter. If 5 implants remain, go for 5 in the bridge.
- Assembling of Balance Base Abutments C/ narrow. Abutment height should be chosen based on mucosa thickness. The recommendation is to place the abutment flange/shoulder epi gingival or even very slightly sub gingival.
- Assembling of Retention Copings for Balance Base Abutments C/ narrow
- Impression, using open-tray and an impression material of high accuracy, becoming stiff after curing
- Disassembling of the Retention Copings
- Closing the screw holes of Balance Base Abutments with wax
- Clinical photos
- Adapting the base of the existing full denture to avoid loading of any of the six implants

*Dental-Lab Work-Flow:*

- Production of master cast
- Production of template for jaw relation recording

#### **5.1.6 Visit 6, Bite registration (IP + 14 weeks, ± 5 days)**

*Clinical Work-Flow:*

- Horizontal and vertical jaw relation record by using the dental lab produced template
- Face-bow transfer

*Dental-Lab Work-Flow:*

- Mounting study casts into articulator (using face bow)
- Production of a wax based esthetic teeth arrangement
- Ordering ATLANTIS ISUS framework
- Production of a try-in of esthetic teeth arrangement based on ATLANTIS ISUS framework

#### **5.1.7 Visit 7, Try in of ATLANTIS ISUS framework + esthetic teeth arrangement (IP + 16 weeks, ± 2 weeks)**

*Clinical Work-Flow:*

- Try in
- New jaw relation record

*Dental-Lab Work-Flow:*

- Finishing the final full-arch bridge

#### **5.1.8 Visit 8, Insertion of final Prosthetic Restoration, PR (IP + 17 weeks, ± 2 weeks)**

*Clinical Work-Flow:*

- Insertion of the final full-arch bridge (for specification of material, see section 8)
- Adaptation of occlusion (canine guided)
- Soft tissue response (Plaque, PPD, BoP)
- Intra-oral x-rays
- Clinical photos
- OHIP-14 to be filled out by the subject

**5.1.9 Visit 9, 6-month Follow-up (PR + 6 months, ± 2 weeks)**

- Clinical photos
- Implant survival
- Soft tissue response (Plaque, PPD, BoP)
- Prosthetic survival
- Prosthetic success

**5.1.10 Visit 10, 12-month Follow-up (PR + 12 months, ± 1 month)**

- Intra-oral x-rays
- Clinical photos
- Implant survival
- Soft tissue response (Plaque, PPD, BoP)
- Prosthetic survival
- Prosthetic success
- OHIP-14

**5.1.11 Visit 11, 24-month Follow-up (PR + 24 months, ± 1 month)**

- Clinical photos
- Implant survival
- Soft tissue response (Plaque, PPD, BoP)
- Prosthetic survival
- Prosthetic success

**5.1.12 Visit 12, 36-month Follow-up (PR + 36 months, ± 1 month)**

- Intra-oral x-rays
- Clinical photos
- Implant survival
- Soft tissue response (Plaque, PPD, BoP)
- Prosthetic survival
- Prosthetic success
- OHIP-14

**5.1.13 Visit 13, 48-month Follow-up (PR + 48 months, ± 1 month)**

- Clinical photos
- Implant survival
- Soft tissue response (Plaque, PPD, BoP)
- Prosthetic survival
- Prosthetic success

**5.1.14 Visit 14, 60-month Follow-up and Study Completion (PR + 60 months, ± 1 month)**

- Intra-oral x-rays
- Clinical photos
- Implant survival
- Implant success
- Soft tissue response (Plaque, PPD, BoP)
- Prosthetic survival
- Prosthetic success
- OHIP-14

**5.2 Compliance**

Subjects will be asked to return to all visits and to follow the Investigator's instructions regarding the treatment at any time (post-surgery activities etc.). Non-compliance is defined as subjects obviously disregarding the Investigator's instructions. Subjects judged to be non-compliant may continue in the study for safety reasons, but the reimbursement of the treatment will be reduced as described in the CSA.

### 5.3 Study population

#### 5.3.1 Selection records

The Investigator(s) must keep a Screening Log of subjects who were considered for inclusion. Subjects listed on that log are either included or failed to fulfill selection criteria, so called 'Screening failures'.

This information is necessary to establish that the subject population was selected without bias.

#### 5.3.2 Identification records

The Investigator(s) must also keep and maintain a Subject Identification Log with e. g. full name, date of birth, subject id etc. of all subjects who have been enrolled and treated within the scope of the study. This information is necessary to be able to identify the participating subjects.

The Subject Identification Log remains on site and will neither be collected nor copied by DENTSPLY Implants.

#### 5.3.3 Subject-selection criteria

##### 5.3.3.1 Inclusion criteria

For inclusion in the study subjects must meet all of the following criteria:

1. Aged 18-80 years at inclusion
2. Signed informed consent
3. In need of full-arch restoration of the maxilla

The following should be considered at inclusion but need to be fulfilled at Implant Placement (Visit 3):

4. Maxilla: totally edentulous, fulfilling all of the following criteria:
  - a) History of edentulism:  $\geq$  6 months and
  - b) Minimum bone height:  $\geq$  7 mm and
  - c) Minimum bone width:  $\geq$  5.5 mm
5. Mandible: antagonistic natural dentition or tooth/implant borne rehabilitation which can be used to create a stable occlusal fit with the new full-arch restoration of the upper jaw

##### 5.3.3.2 Exclusion criteria

Any of the following is regarded as a criterion for exclusion from the study:

1. Unlikely to be able to comply with study procedures according to Investigators judgement
2. History of bone augmentation in the maxilla within 6 months prior to surgery
3. Uncontrolled pathologic processes in the oral cavity
4. Bruxism
5. Smoking >10 cigarettes per day
6. Present alcohol or drug abuse
7. History of radiation therapy in head and neck region
8. History of chemotherapy within 5 years prior to surgery
9. Condition that would compromise post-operative tissue healing or osseointegration
10. Bisphosphonates or any other medication that would compromise post-operative healing or osseointegration.
11. Known pregnancy at time of inclusion
12. Current or former participation in a clinical study that may interfere with the present study
13. Involvement in the planning and conduct of the study

## 5.4 Restrictions

Restrictions regarding hygiene measures, use of subject's existing prosthesis and food intake will be given in accordance with the clinic's local routines.

## 5.5 Discontinuation of subjects from study

### 5.5.1 Criteria for discontinuation

Subjects may be discontinued from the study at any time. Specific reasons for discontinuing a subject include:

- Voluntary discontinuation by the subject who is at any time free to discontinue his/her participation in the study, without prejudice to further treatment
- Safety reasons as judged by the Investigator or the sponsor
- Severe non-compliance to the CIP as judged by the Investigator and/or the sponsor
- Subject lost to follow-up (as defined by the inability to reach the subject after 3 attempts to contact him/her, e.g. by phone, email, or letter; all should be documented in the subject's medical records)
- Loss of all study implants

### 5.5.2 Procedures for discontinuation

Subjects who discontinue should always be asked about the reason(s) for their discontinuation and the presence of any safety issues. If possible, they should be seen and assessed by an Investigator. The Termination section in the eCRF should be completed. AEs should be followed up.

After discontinuation, appropriate further treatment will be initiated according to the Investigator's judgment and according to local medical practice.

### 5.5.3 Procedure for handling enrolled subjects that fail to fulfill inclusion/ exclusion criteria

If a subject has been enrolled, but no study-related surgical procedures were performed (withdrawal of consent, not meeting all pre-surgical criteria etc.) the Investigator must document this in the subject's medical records. In case of the subject's unavailability the Investigator will document this as well. Termination section in the eCRF should be completed. No follow-up is necessary.

If a subject has been enrolled and study-related surgery started, but for any reason no Investigational Product could be inserted the Investigator must document this in the subject's medical records. Termination section in the eCRF should be completed. No follow-up is necessary.

If a subject has been enrolled and study-related surgery has been completed, although the inclusion/exclusion criteria are violated, it will be decided on a case-by-case basis by DENTSPLY Implants if the subject will continue in the study. If so, the subject will not be part of the Intention-to-Treat (ITT) analysis and the reimbursement of the treatment will be reduced as described in the CSA.

If a subject lose a study implant and a new implant is inserted, the new implant should not be registered in the eCRF. If a subject loses all study implants, the subject will discontinue the study.

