##### 6.3.1.1 Assessment of primary outcome variable

Implant survival will be evaluated clinically and radiographically by counting the number of implants remaining *in situ*. Any implant that has been removed or lost after implant placement (Visit 3) will be considered a failure, whatever the reason for removal/loss.

Implant survival rate will be analyzed on an implant level (i.e. percent of survived implants) as well as subject level (i.e. percentage of subjects with no lost implants).

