OHIP-14 includes seven domains and is therefore able to cover a wide range of possible oral health problems that may have an impact on quality of life. The domains are: functional limitation, pain, psychological discomfort, physical disability, psychological disability, social disability and handicap. OHIP attempts to measure both the frequency and severity of oral problems on functional and psychosocial well-being. An example of an OHIP statement is "Have you had to interrupt meals because of problems with your teeth, mouth or dentures". Responses are based on a Likert scale (i.e., 0 = never, 1 = hardly ever, 2 = occasionally, 3 = fairly often, 4 = very often).

- ***Implant success***

Implant success will be evaluated as defined by the ICOI Pisa Consensus Conference 2008 [35]. An implant will be considered successful if all of the following criteria are fulfilled:

- Implant still in place
- No mobility
- No pain or tenderness upon function
- <2 mm marginal bone loss from initial surgery to 5-year follow-up visit
- No history of exudates

- ***Prosthetic survival***

A prosthetic restoration will be considered a *survivor* if the original restoration is still in place at the follow-up visit, regardless of its condition.

- ***Prosthetic success***

A prosthetic restoration will be considered as successful if it has remained unchanged and there has been no need of technical repair during the observation period.

The occurrence of any technical repair of the prosthesis or any biological complications related to the prosthesis will be registered and reported as ADEs (section 6.4.1.2).

- ***Number of avoided augmentations***

The proportion of augmentations avoided by using six 6.6 mm implants instead of six 8.0 mm implants will be virtually evaluated by using the SIMPLANT file generated from the CBCT at Visit 2. First, six regions of interest will be defined in SIMPLANT by indicating the mesial and distal borders of the canine, premolar and molar regions on both left and right side. An evaluator, independent from the investigational group and DENTSPLY Implants, will then make a surgical planning with six 6.6 mm implants placed at the pre-defined canine, premolar and molar regions and count the number of sites that would need augmentation. The evaluator will then repeat this

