## 10.3 Method of statistical analysis in relation to objectives

If nothing else is stated, descriptive statistics will be given for each variable in the study and p-values may be complemented by confidence intervals as appropriate.

All p-values presented will be two-sided. A p-value less than 5% will be called “statistically significant” but all conclusions will be based on the primary objective and hence multiplicity is accounted for even though careful interpretations are necessary as multiple tests are performed. No formal adjustment for multiplicity will be applied and nominal p-values will be presented. All confidence interval will be two-sided and 95%.

When calculating p-values a non-parametric statistical approach will be applied because of the nature of the data. Confidence interval will be calculated using distribution assumptions.

The primary objective will be analysed using the exact Binomial test and a parametric confidence interval for the true proportion of implants surviving will be presented

The safety profile will be analysed using descriptive statistics only.

The planned statistical methods for the efficacy evaluation is presented by objective below:

Primary Objective	Corresponding Primary Outcome Variable	Statistical Method
Implant survival	Implant in situ during study	The exact Binomial test and a parametric confidence interval for the true proportion of implants surviving will be presented

Secondary Objective(s)	Corresponding Secondary Outcome Variable(s)	Statistical Method
Implant stability	Stability	A parametric confidence interval for the true proportion of implants with stability = “yes” will be presented
Bone tissue response	Marginal Bone Level (MBL)	The change over time will be tested using the Wilcoxon signed rank test and a parametric confidence interval presented.
Soft tissue response	Plaque, Probing Pocket Depth (PPD) and Bleeding on Probing (BoP)	The change over time will be tested using the Wilcoxon signed rank test and a parametric confidence interval presented.
Patient reported outcomes	OHIP-14	The change over time will be tested using the Wilcoxon signed rank test and a parametric confidence interval presented.

Secondary Objective(s)	Corresponding Secondary Outcome Variable(s)	Statistical Method

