## Appendix B: Visit and procedure plan

	Visit 1	Visit 2	Visit 3	Visit 4	Visit 5	Visit 6	Visit 7	Visit 8	Visit 9-14
	Screening and Inclusion	Pre-surgical planning	Implant Placement (IP)	Post-op Check	Abutment Surgery and Impression	Bite Registration	Try-in	Permanent Restoration (PR)	Follow-up
				IP+7-10 days	IP+13 weeks (±10 days)	IP+14 weeks (±5 days)	IP+16 weeks (±2 weeks)	IP+17 weeks (±2 weeks)	PR+6, 12, 24, 36, 48 and 60 months (±1 month)
Subject eligibility	X	X	X						
Written Informed Consent	X								
Subject demographics	X								
Oral examination	X								
CBCT		X	X						
OHIP		X						X	X a
Implant stability			X		X				
Clinical photos	X		X		X			X	X
Intraoral X-rays								X	X b
Plaque, PPD, BoP								X	X
AE documentation		X	X	X	X	X	X	X	X

a OHIP at Visit 10, 12 and 14b Intraoral X-rays at Visit 10, 12 and 14

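### Subjects who lose all study implants must leave the study, so OHIP-14 at later visits leaves out the complete treatment failures

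*Combined protocol and SAP*

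**What the plan says.** **Discontinuation.** Section 5.5.1 lists "Loss of all study implants" among the specific reasons for discontinuing a subject. Section 5.5.3 makes it mandatory: "If a subject loses all study implants, the subject will discontinue the study". At discontinuation, Section 5.5.2 asks for the reason and any safety issues, completion of the eCRF termination section and follow-up of adverse events. On any other assessment it says only: "If possible, they should be seen and assessed by an Investigator". It names neither OHIP-14 nor a prosthetic assessment.

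**OHIP-14.** The questionnaire is completed at Visits 2 and 8. For follow-up, the footnote in Appendix B reads: "OHIP at Visit 10, 12 and 14". The analysis in Section 10.3 is: "The change over time will be tested using the Wilcoxon signed rank test and a parametric confidence interval presented".

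**Missing data.** Section 10.1.3 covers two things only: replacement of subjects who drop out while recruitment is open, and an allowance in the sample size for those who drop out later. It has no rule for missing scores and no exception for subjects who leave because treatment failed.

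**Implants and restorations.** For the primary outcome, Section 6.3.1.1 is clear: "Any implant that has been removed or lost after implant placement (Visit 3) will be considered a failure, whatever the reason for removal/loss". Under Section 6.3.2.2 a restoration survives "if the original restoration is still in place at the follow-up visit, regardless of its condition" and is successful "if it has remained unchanged and there has been no need of technical repair during the observation period".

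**The concern.** Losing all six implants is the worst outcome this treatment can have. The plan makes that outcome the trigger for ending data collection, so later OHIP-14 scores are missing because treatment failed. A signed rank test on change needs a score at both times. With no other rule in the plan, the analysis at later visits uses only subjects who still have at least one study implant.

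The rule is also stricter here than elsewhere. Non-compliant subjects may stay in the study (Section 5.2), and subjects treated despite violating the entry criteria may stay case by case (Section 5.5.3). Complete implant failure is the case with no discretion.

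OHIP-14 matters because Section 1.2 gives patient satisfaction with a fixed bridge as one of the two advantages that the study combines. At stake is whether the 5-year OHIP-14 change describes everyone treated or only those whose treatment did not fail completely.

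**Working it through.** **1. The plan's own figure.** Section 10.4 needs 304 implants for 90% power with an exact one-sided 0.025 binomial test, null survival 0.90 and true survival 0.95. Rejecting when at least 284 of 304 survive gives an exact type I error of 0.0243 and power of 0.914, so the figure reproduces. Then 304/6 = 50.7, or 51 evaluable subjects. Allowing for 10% dropout, 51/0.9 = 56.7 against the plan's 56, a difference with no bearing here. None of this depends on the discontinuation rule.

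**2. What the text does with a subject who loses all six implants after Visit 8.**

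| Outcome | Treatment under the plan |
|---|---|
| Implant survival | Six failures counted (6.3.1.1) |
| OHIP-14 before the loss | Kept |
| OHIP-14 after the loss | Not collected; no rule for the gap |
| Prosthetic survival and success | Failure is known, but scoring at visits that do not take place is not stated |
| Analysis set | Stays in the ITT set, which requires eligibility and implants installed as planned (10.2) |

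**3. How many such subjects to expect.** The assumed true survival of 93% to 95% (Section 10.4) gives a per-implant loss q of 0.05 to 0.07. Under the plan's independence assumption, P(all six lost) = q^6. With within-subject correlation ρ (an assumption; the documents give none), a beta-binomial with s = (1 − ρ)/ρ gives P = product over i = 0 to 5 of (qs + i)/(s + i). For q = 0.05 and ρ = 0.5, s = 1:

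P = (0.05/1)(1.05/2)(2.05/3)(3.05/4)(4.05/5)(5.05/6) = 0.00932, and 56 × 0.00932 = 0.52.

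| ρ (assumed) | q = 0.05: expected of 56 | P(at least one) | q = 0.07: expected of 56 | P(at least one) |
|---|---|---|---|---|
| 0 (plan) | 0.0000009 | 0.0000009 | 0.000007 | 0.000007 |
| 0.1 | 0.003 | 0.003 | 0.007 | 0.007 |
| 0.3 | 0.12 | 0.11 | 0.19 | 0.17 |
| 0.5 | 0.52 | 0.41 | 0.76 | 0.54 |
| 1 (complete clustering) | 2.8 | 0.94 | 3.9 | 0.98 |

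**4. Effect on OHIP-14.** If k of N subjects are left out and their mean change differs from the rest by a gap g, the reported mean shifts by (k/N) × g. The documents give no gap, so g = 10 to 20 points is an assumption.

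- k = 1, N = 56: 10/56 = 0.18 to 20/56 = 0.36.
- k = 1, N = 51 evaluable: 10/51 = 0.20 to 20/51 = 0.39.
- k = 3, N = 56: 30/56 = 0.54 to 60/56 = 1.07.

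**5. Range left open by the missing prosthetic scoring rule.** With 56 restorations and no other failures (assumption), one complete loss gives 55/56 = 98.2% if scored as a failure and 55/55 = 100% if left unscored. Two give 54/56 = 96.4% against 100%. These are the two ends of what the text permits, not a predicted bias.

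**The case against.** The strongest reply is that stopping OHIP-14 when no study implant remains is a legitimate choice. Section 6.3.2.2 places the questionnaire before and after implant treatment, and Section 5.5.2 provides for further treatment after discontinuation. Later scores would partly measure that other treatment. This is a fair argument about the target of estimation, and it stands as a reason to state the choice and add a sensitivity analysis. It does not justify leaving the choice unstated, because the plan neither restricts the OHIP-14 result to time with study implants nor says how the missing scores are handled.

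It is also said that the event is rare and the outcome secondary. Both are true. Section 1.2 puts the main interest in implant survival and success, and Section 10.3 rests all conclusions on the primary objective.

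A reader might infer more than the documents support:

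- *That the prosthetic rates lose these failures.* The bridge is screw-retained on the study implants (Section 8), so with none left it cannot be in place. Implant loss is recorded as an adverse device effect (Sections 6.4.1.5 and 6.4.2), and the subject stays in the ITT set. What is missing is a scoring rule. A loss before Visit 8 leaves no final restoration to score.
- *That all results describe only subjects who kept an implant.* Only OHIP-14 at visits after the loss is missing.
- *That two or more subjects should be expected.* Dividing about 15 failures (304 × 0.05) by six gives 2.5, but only if nearly all failures fall in the same few mouths.
- *That the shift is always favourable.* Scores after further treatment could be good or poor.

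**Conclusion.** The point holds for OHIP-14 and is minor. Followed as written, the plan creates missing OHIP-14 data as a direct result of complete treatment failure, and it has no rule for handling them. The primary test is not affected.

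The most likely number of such subjects is zero or one. It is practically nil under independence, 0.1 to 0.8 of 56 at ρ = 0.3 to 0.5, and 2.8 to 3.9 only with complete clustering. One subject moves the mean OHIP-14 change by about 0.2 to 0.4 points. The correlations and the 10-to-20-point gap are assumptions. The direction is probably favourable to the treatment, but the documents do not establish it.

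Two related gaps are matters of clarification, not shown bias: how the restoration is scored after complete loss, and whether a subject who loses all implants while recruitment is open would be replaced as a dropout under Section 10.1.3.

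**What to change.** - **Sections 5.5.1 and 5.5.3:** state that loss of all study implants ends implant-level assessments only. Keep collecting OHIP-14 at whichever of Visits 10, 12 and 14 remain, by post or telephone if the subject prefers. Follow-up visits are timed from insertion of the restoration, so also state the reference date for a subject who loses all implants before Visit 8. This concerns data collection only and leaves the provisions on further treatment in Section 5.5.2 untouched.
- **Section 10.3:** include these scores in the OHIP-14 change analysis, with a sensitivity analysis that uses only scores before the loss.
- **Section 6.3.2.2:** score an inserted restoration as not surviving and not successful from the date of loss. Report losses before Visit 8 separately, since there is no restoration to score.
- **Section 10.1.3:** state that such subjects are not replaceable dropouts and stay in the analysis, and report their number.

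The cost is a few sentences of protocol text and up to three questionnaires per affected subject. The downsides are slightly less favourable secondary figures and later OHIP-14 scores that reflect any further treatment, which the sensitivity analysis addresses.
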